## **A. SPECIFIC AIMS/ OBJECTIVES**

This clinical research trial aims to study the efficacy and safety of cannabidivarin (CBDV), a naturally occurring homolog of the phytocannabinoid cannabidiol (CBD) in children and young adults with Prader-Willi Syndrome (PWS). CBDV has affects independent of CB1 and CB2 receptor activation and a good safety profile. This proposal addresses the Foundation for Prader-Willi Research's five-year PWS Research Plan- Program 1, Clinical Care Research: seeks to evaluate treatments that aim to reduce behavioral symptoms, such as irritability, in order to improve the quality of life of both the individual with PWS and their families. GW Pharmaceuticals will provide the CBDV drug, matching placebo and additional funding to the site.

### **Primary Aim**

To compare CBDV vs. placebo on change in irritability from baseline to endpoint using the Aberrant Behavior Checklist-Irritability Subscale (ABC-I).

### **Secondary Aims**

To compare CBDV vs. placebo on changes from baseline to endpoint in:

1. Repetitive behaviors using the Repetitive Behavior Scale – Revised (RBS-R) and the Children's Yale- Brown Obsessive Compulsive Scale (CY-BOCS).
2. Hyperphagia using the Hyperphagia Scale for Clinical Trials (HQ-CT)
3. Sleep quality using ActiGraph GT9X-BT activity monitors.
4. Rigid behaviors using the Montefiore-Einstein Rigidity Scale-Revised-PWS (MERS-R-PWS)
5. Global improvement using the Clinical Global Impressions Scale-Improvement (CGI-I) and Caregiver Strain Questionnaire (CSQ).
6. ABC subscales in lethargy/social withdrawal, stereotypic behavior, hyperactivity/noncompliance, and inappropriate speech

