## **C.8. Definition of Primary and Secondary Outcomes/Endpoints**

### **I. Outcome measures**

Project outcomes will be determined by changes in score of parent and clinician rated measures from baseline to week 12 and comparisons of week 12 measures between active treatment and placebo groups. Assessments will be administered according to the schedule in Table 1. Future studies may incorporate additional long-term maintenance studies to provide more data on safety and efficacy. Additions measures will be completed per Schedule of Events.

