## V. Clinical Global Impression Scale – Improvement (CGI-I):

The CGI-I will be used as a measure of improvement and contains a 7-point scale as follows: 1 = very much improved, 2 = much improved, 3 = minimally improved, 4 = no change, 5 = minimally worse, 6 = much worse, 7 = very much worse. The CGI-I is a clinician rated global measure of improvement and has been used as a measure in previous clinical psychopharmacology trials that takes 5 minutes to complete.

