### **C.8.3. Other Assessments**

#### **I. Clinical Global Impression-Severity (CGI-S)**

The CGI-S reflects the rater's impression of the subject's current illness state on a 7-point scale ranging from no symptoms (1) to very severe (7). Whenever possible, for any individual, these assessments should be done by the same rater throughout the study.

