### **III. Baseline (visit 1, week 1, in-person)**

At the baseline visit, subject will be re-consented. Repeat drug and pregnancy test (if applicable) will be done. In the case of positive result, testing will be repeated for confirmation. Confirmed positive results will lead to exclusion.

For subjects who continue to meet study criteria, study clinician will review concomitant medications, obtain vital signs, weight, BMI, IQ test, ABC, RBS-R, CY-BOCS, Actigraphy Remote sleep measurement, Caregiver Strain Questionnaire, CGI-S, HQ-CT, MERS-R-PWS and C-SSRS. Body composition will be assessed using bio-impedance analysis. A physical and neurological exam will be performed. ECG will be done. Safety labs including CBC, BMP, LFT, and concomitant plasma drug levels of valproic acid, lamotrigine, oxcarbazepine, phenytoin and clobazam for those patients who take them will be drawn. Dietary diary will be completed by participant and reviewed. Blood sample will be collected and preserved for biorepository for consented patients. Actigraphy data collected prior to in person visit will be reviewed.

For subject that meet all inclusion/exclusion criteria after all assessments, they may enroll and be randomized to a study group at this visit. The study pharmacist at the Clinical Research Pharmacy will use a computer-generated randomization table to randomize subjects in a 1:1 ratio.

Enrolled patients will receive a weight-based dosing up to 10 mg/kg/day of CBDV (max 800 mg/day) or placebo for 12 weeks on a titration schedule as specified in protocol, administered b.i.d with food.

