### **G. DATA ANALYSIS PLAN**

Subject will be randomly assigned (1:1) to CBDV or placebo and followed for 12 weeks. Analyses will be based on the intent-to-treat approach in which subjects are analyzed in the group to which they were originally assigned regardless of compliance. The demographic characteristics of all randomized patients will first be summarized using standard descriptive statistics (means, medians, standard deviations, and ranges for continuous variables and frequencies for categorical variables). Our primary analysis will examine CBDV vs. placebo on the ABC-I. Our secondary analyses will investigate changes in measures of repetitive behaviors (RBS-R, CYBOCS), hyperphagia (HQ-CT), sleep quality (ActiGraph activity monitors), rigid behaviors (MERS-R-PWS), problematic behaviors (other ABC subscales) and global improvement (CGI-I, CGI-S, CSQ). Between group differences in these measures obtained at a specific time point (e.g. 12 weeks) will be compared with the two sample t-test or Wilcoxon rank sum test. In addition, the change in outcome measures between baseline and 12 weeks will be compared between treatment groups. Exploratory analyses will first be performed to evaluate whether the magnitude of changes in these variables between the two time points depends on the baseline value. If there is no evidence that change is dependent on baseline, then two sample t- tests will be used to compare the mean change in each variable between treatment groups; otherwise, analysis of covariance models will be fit to the data where the outcome is the level measured at 12 weeks, and the main effects are treatment group and baseline value. Adjustment for any patient characteristics which appear to be imbalanced across treatment groups will be accomplished by including the relevant terms as main effects into the model. To compare longitudinal trends in outcomes between treatment groups, linear fixed effects models will be fit to all repeated measures obtained during follow-up, with main effects for time and treatment group and a time x treatment interaction term; this is a widely used statistical approach in longitudinal studies of psychiatric outcomes. Appropriate data transformations, such as the log transform, will be applied if the data deviate from the normal distribution.

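### CGI-I is assigned change-from-baseline and own-baseline ANCOVA steps that are undefined for it; one week-12 analysis adjusted for baseline CGI-S should be named instead

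*Combined protocol and SAP*

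**What the plan says.** Section A introduces the whole list of Secondary Aims with "To compare CBDV vs. placebo on changes from baseline to endpoint in", and item 5 of that list is "Global improvement using the Clinical Global Impressions Scale-Improvement (CGI-I) and Caregiver Strain Questionnaire (CSQ").

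Section C.8 (Outcome measures) defines outcomes in two ways: as score changes from baseline to week 12, and as "comparisons of week 12 measures between active treatment and placebo groups".

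Section G says the secondary analyses will look at changes in a set of measures that includes CGI-I, CGI-S and CSQ. It plans these analyses without distinguishing between measures:

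- a two-group comparison at a given time point, such as week 12, by t-test or Wilcoxon rank sum test;
- a change analysis: "the change in outcome measures between baseline and 12 weeks will be compared between treatment groups". An exploratory check of whether change depends on baseline comes first. It decides between a t-test on change and an ANCOVA of the week-12 level on treatment and baseline value;
- extra covariates only for characteristics that look imbalanced between arms;
- a longitudinal model on all follow-up measurements, with time, treatment and their interaction.

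Section C.8.2 describes the scale: "The CGI-I is a clinician rated global measure of improvement", scored "1 = very much improved, 2 = much improved, 3 = minimally improved, 4 = no change", with 5 to 7 for worsening. Section C.8.3 describes its companion: "The CGI-S reflects the rater's impression of the subject's current illness state on a 7-point scale". The baseline visit in Section C.9.2 collects "Caregiver Strain Questionnaire, CGI-S, HQ-CT, MERS-R-PWS and C-SSRS" among other scales, but not CGI-I. The Schedule of Events (C.10) marks CGI-I at weeks 4, 8, 12 and 14 only.

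**The concern.** A change score and an own-baseline ANCOVA both need a pre-treatment value on the same scale. CGI-I has none, and it could not have one, because each rating already describes change since the start. Section G makes no exception for it. An analyst who follows the text reaches CGI-I and finds that three of the listed steps cannot be carried out, with no instruction on what replaces them.

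What remains is open to choice. There is no rule for choosing between the t-test and the Wilcoxon test on a 7-point ordinal scale, and nothing says whether that test or the longitudinal model answers aim 5. CGI-S is a rating of state and is recorded at baseline, so it is the natural baseline covariate for CGI-I, but the plan does not name it in that role. At stake is how clearly one secondary outcome is prespecified, along with a modest amount of precision.

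**Working it through.** **Which planned steps can be run.** Set the steps in Section G against the baseline visit list in C.9.2 and the schedule in C.10:

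| Step in Section G | Needs a baseline on the same scale? | CGI-I | CGI-S, CSQ |
|---|---|---|---|
| Week-12 t-test or Wilcoxon | No | Can be run | Can be run |
| Change from baseline to week 12 | Yes | Undefined | Can be run |
| Check that change depends on baseline | Yes | Undefined | Can be run |
| ANCOVA on own baseline | Yes | Undefined | Can be run |
| Longitudinal model on follow-up data | No | Can be run (from week 4) | Can be run |

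CGI-I has no mark at screening or baseline, so the number of patients with a baseline CGI-I is 0 of 36 by design. This is not a missing-data problem.

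**Filling in a baseline does not help.** Suppose every patient is given a baseline of 4 (no change). The arm difference in change is then (mean CBDV − 4) − (mean placebo − 4) = mean CBDV − mean placebo, which is simply the week-12 comparison. In the ANCOVA, a covariate equal to 4 for everyone is collinear with the intercept, so its slope cannot be estimated.

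**The longitudinal model.** For CGI-I the first observation is at week 4. The time-by-treatment term therefore describes divergence after week 4, and any effect already present by then falls into the treatment term. The plan does not say which term would answer aim 5.

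**The plan's sample size, which supplies the group size used below.** Section H gives a difference of 8.26, an SD of 8.27, two-sided alpha 0.05 and 80% power for ABC-I:

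n per arm = 2 × (1.960 + 0.842)² × (8.27 / 8.26)² ≈ 15.7, rounded up to 16, so 32 in total.

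Power at 16 per arm is 0.806 by normal approximation and 0.780 by t-test. With 10% drop-out, 32 / 0.9 = 35.6, rounded up to 36. The stated 32 and 36 are reproduced. The protocol gives no sample-size figure for CGI-I.

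**What adjustment for baseline CGI-S could gain.** With 16 per arm, an unadjusted week-12 t-test has 80% power for a standardized difference of about 1.02. If r is the correlation between baseline CGI-S and week-12 CGI-I, residual variance is multiplied by 1 − r² and the detectable difference by √(1 − r²). The documents give no r, so the values below are assumptions:

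| Assumed r | 1 − r² | Fall in residual variance | Detectable standardized difference |
|---|---|---|---|
| 0 | 1.00 | 0% | 1.02 |
| 0.1 | 0.99 | 1% | 1.02 |
| 0.2 | 0.96 | 4% | 1.00 |
| 0.3 | 0.91 | 9% | 0.98 |
| 0.4 | 0.84 | 16% | 0.94 |

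These figures ignore the one degree of freedom spent on the covariate. They come from a linear model, so they are only a guide for a rank-based or ordinal analysis. Inclusion criterion 6 requires CGI-S of at least 4, which limits the covariate to 4 to 7 and may keep r towards the low end.

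**The case against.** The strongest reply is that nothing of substance is lost. CGI-I is a rating of change, so comparing week-12 ratings between arms is a comparison of change to endpoint, and aim 5 calls it global improvement. Section C.8 expressly includes week-12 comparisons. Section G lists the time-point test first and brings in the change score as an addition. Treatment is randomized 1:1, so the unadjusted comparison is valid. The trial is a pilot that the plan calls exploratory, and the primary ABC-I analysis is untouched.

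Most of this stands, and it rules out three stronger readings that a reader might infer:

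- *That CGI-I has no usable analysis, or that aim 5 cannot be delivered.* The week-12 test and the longitudinal model both run on CGI-I.
- *That baseline CGI-S goes unused.* It is an entry criterion in C.2 and a listed outcome in Section G, where its baseline enters its own analysis. It could also be added as a covariate if the arms looked imbalanced.
- *That CGI-I is the main check on the caregiver-rated ABC-I.* The protocol never says so, and CY-BOCS, MERS-R-PWS and CGI-S are also clinician-rated.

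The reply does not remove the mismatch itself. The change and own-baseline steps are written for CGI-I without exception, and they are impossible for it. Calling the study exploratory explains why multiplicity is not adjusted for. It does not tell the analyst which CGI-I analysis to report.

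**Conclusion.** The point holds, and it is minor. For CGI-I the change score, the baseline-dependence check and the own-baseline ANCOVA are undefined for all 36 planned patients. This follows from the scale's definition and the schedule and needs no assumption. Other planned analyses of CGI-I can be run, so the defect is an inapplicable instruction and a loosely specified replacement.

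Baseline CGI-S is not prespecified as a covariate for CGI-I. The benefit of adding it is small to moderate and rests entirely on an assumed correlation: about 1% to 16% less residual variance for r from 0.1 to 0.4, which would lower the detectable standardized difference from about 1.02 to at best 0.94 within that range. The primary analysis and sample size do not change.

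**What to change.** In Section A and Section G, take CGI-I out of the change-from-baseline, baseline-dependence and own-baseline ANCOVA steps. State that its analysis is the between-arm comparison of the week-12 rating, by one prespecified method adjusted for baseline CGI-S. This can be a rank-based comparison or an ordinal model such as proportional odds. With about 16 patients per arm on a 7-point scale, an ordinal model needs a rule, fixed before unblinding, for collapsing sparse categories. The proportion rated 1 or 2 can be reported alongside as a descriptive summary. If the longitudinal model is also kept for CGI-I, say that it is supportive and which term is read.

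Keep the change or ANCOVA analysis for CGI-S and CSQ, which have baseline values. Align the two sections on CGI-S, which Section G lists as an outcome and the Secondary Aims omit.

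The cost is a wording change and one covariate in about 32 evaluable patients. Both scales are already collected, so no visit, assessment or sample-size change is needed.

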## **B. BACKGROUND and SIGNIFICANCE**

There is an unmet need for therapeutics to treat the diverse symptoms of Prader-Willi Syndrome (PWS). Irritability (often manifested along with temper tantrums, anxiety and rigid behavioral patterns) is a primary characteristic of PWS that significantly disrupts the daily functioning of children and young adults with PWS and their families. Despite the substantial burden that irritability engenders, it has not been systematically examined as an outcome in clinical treatment

trials of children and young adults with PWS. The significance of reducing irritability in patients with PWS cannot be over-stated, as it would substantially improve not only the quality of life for the patient but their caregivers and family as well. CBDV is well suited to address this target symptom in PWS.

## **I. Key Features of PWS**

PWS is a neurodevelopmental disorder caused by loss of paternally expressed genes from the 15q11-q13 region. PWS symptoms include irritability, restricted and repetitive behaviors, hyperphagia, sleep disturbances and seizures. PWS individuals may also exhibit immune-inflammatory alterations associated with GABAergic dysfunction, which contributes to hyperphagia. Seizures in PWS may be associated with immune dysfunction, inflammation and altered cytokines.

## **II. CBDV Mechanisms and Therapeutic Potential**

CBDV is a component of cannabis and a naturally occurring homolog of cannabidiol (CBD). Unlike Δ9-THC, CBDV lacks appreciable affinity and functional activity at CB1 or CB2 receptors. Instead, it is a multi-target drug which interactions include inhibition of the equilibrative nucleoside transporter (ENT) and the orphan G-protein-coupled receptor GPR55. CBDV is also an agonist of multiple transient receptor potential (TRP) channels, including TRPV1, TRPV2, TRPV4, and TRPA1 and is an antagonist of TRPM8. Additionally, CBDV has anti-inflammatory effects and has a potential to act as an analgesic. In a maternal immune activation (MIA) model of neurodevelopmental disorders, repetitive behaviors are alleviated by anti-inflammatory treatment, suggesting that CBDV may alleviate repetitive behaviors in PWS. In PWS increased excitatory-inhibitory (E-I) ratio due to altered GABA-glutamate neurotransmission can result in seizures, behavioral changes and social dysfunction. CBDV has well-established anticonvulsant effects in animal models.

Across all GW sponsored Phase 1 and Phase 2 clinical trials with CBDV to date, CBDV was generally well tolerated in adults at doses of up to 1600 mg/day; most adverse events (AEs) were considered mild or moderate in severity and the incidence of serious treatment-emergent adverse events (TEAEs) was low

The potential therapeutic mechanisms of CBDV in humans with PWS can be inferred from its neurobiological effects, and from the effects of the related compound, CBD on epilepsy, addiction, anxiety, depression and schizophrenia. CBDV has the potential to be a valuable therapeutic agent for PWS by virtue of its anti-inflammatory, anti-oxidative, neuro-protective, anti-anxiety and anticonvulsant properties. CBDV, similarly to CBD, may modulate sleep that is often disturbed in PWS and may play a role in food regulation and hyperphagia. With its effects on multiple mechanisms known to be dysfunctional in PWS and low side effect profile, CBDV is a promising treatment that needs further exploration in this population.

## **III. CBDV and Irritability in PWS**

Individuals with PWS frequently exhibit irritability, which manifests as a consequence of emotion dysregulation, disruption of rigid behavioral patterns or excessive response to stimuli. Irritability is a well-characterized outcome that has been accepted by the FDA for the purposes of labeling in other cohorts. The FDA has approved treatments for irritability in ASD, including aripiprazole and risperidone, based on the Aberrant Behavior Checklist (ABC) – Irritability subscale.

In animal models of neurodevelopmental disorders, CBDV has been shown to reduce hyperactivity, which may be suggestive of an improvement in irritability.

#### **IV. CBDV and Repetitive/Restricted Behaviors in PWS**

Rigidity and repetitive behaviors (RRB) are key symptoms of PWS. RRBs are also found in other addictive and neurodevelopmental conditions. CBDV reduced repetitive grooming in Valproic-Acid (VPA) treated male rats, a model of autism that is analogous to the RRB in PWS. Therefore, it can be hypothesized that CBDV may also reduce RRBs in PWS. Our use of the Repetitive Behavior Scale-Revised (RBS-R), a reliable and valid scale containing six subscales (Stereotyped; Self-Injurious; Compulsive; Ritualistic; Sameness; and Restricted behaviors), will allow us to clarify the impact of CBDV on distinct subdomains of RRB.

#### **B.1. Preliminary studies**

##### **1. Effects of CBDV (2-200mg/kg ip) in Animal Models of Genetic Disorders**

Behavioral deficits in the MECP2 KO Mouse, a model of Rett Syndrome, were attenuated with CBDV (2, 20 and 200mg/kg i.p.). CBDV is also shown to delay neurobehavioral deficits observed in MECP2 KO mice including tremor, breathing, and general condition but appears to have limited effect on impaired motor function. CBDV also reverses short term and long term cognitive deficits observed in MECP2 KO mice. These effects of CBDV do not appear to be dose related.

FMR1 KO mice, a model of Fragile X Syndrome, also have attenuation of behavioral deficits with CBDV treatment. CBDV (100 and 200 mg/kg i.p.) attenuates audiogenic seizures in the FMR1 KO mouse following acute administration, while CBDV (20 and 100 mg/kg i.p.) attenuates a deficit in visual recognition memory (NOR) following sub-chronic (but not acute) administration in the FMR1 KO mouse.

##### **2. Effects of CBDV on Behavioral Deficits in the Rat Valproate (VPA) Model:**

The VPA animal model displays some of the neurobehavioral deficits and pathophysiology observed in the brains of individuals with developmental disorders. Male rats prenatally exposed to VPA were treated with CBDV (2, 20, and 100 mg/kg, i.p).

##### **3. CBDV Clinical Studies:**

CBDV has been dosed up to 1600 mg, given as 800 mg BID in patients with focal seizures for 8 weeks. In healthy volunteers the maximum single dose administered was 20 mg/kg and the maximum daily dose 40 mg/kg.

Over the dose range 5 to 20 mg/kg (single dose), CBDV median  $t_{max}$  values ranged from 2.5 to 5 hours. Biphasic absorption was evident at higher doses. Exposure to CBDV and its main metabolites, 7-OH-CBDV and 7-COOH-CBDV, increased in a dose-proportional manner.

CBDV  $C_{max}$  and AUC (0-t) increased approximately 4- and 6-fold, respectively, when CBDV was taken with a high-fat/high-calorie meal, compared with fasted dosing; the AUC (0-t) of 7-OH-CBDV increased by approximately 3-fold and the AUC(0-t) of 7-COOH-CBDV remained stable.

There is limited clinical data available on CBDV. Unacceptable adverse reactions may develop at any time. With other cannabinoid medicines, AEs are typically mild in severity and resolve in a few days. Please refer to CBDV IB for further details. CBDV was noted to cause an asymptomatic transaminase

increase without an increase in bilirubin in a Phase 1 healthy volunteer study. For this reason, the maximum dose of CBDV advised is 20 mg/kg/day in patient studies.

#### **4. Irritability in PWS:**

We recently completed a study comparing oxytocin vs. placebo in 23 children and adolescents with PWS. The mean ABC-I score was 17 at baseline, and 39% (9/23) had an ABC-I score of  $\geq 18$  at baseline. Improvement in the Caregiver Strain questionnaire was correlated with improvement in irritability on the ABC-I ( $r=.61$ ,  $p=.058$ ). Thus, our data supports high levels of irritability in children with PWS, and the impact of improvement in irritability on quality of life.

